10.2 Recording and reporting AEs and SAEs

The Sponsor expects that adverse events are recorded from the point of Informed Consent. Given the remote nature of this study, we do not expect there to be a large number of adverse events.

There are no expected SAEs for this study.

10.3 Reporting Responsibilities

Adverse events experienced by study participants will be recorded, followed-up and reviewed by an investigator as per the CETU SOP for recording and reporting adverse events. The Operational Group will monitor the frequency and type of adverse events during each of their scheduled meetings. In addition, the monthly CETU Steering Group Meeting will receive a report on the numbers of adverse events recorded during the previous month.

All Serious Adverse Events will be reported to the Chief Investigator using the CETU SAE form within 24 hours of awareness of the event. The Chief Investigator is responsible for ensuring the assessment of all SAEs for expectedness and relatedness is completed and the onward notification of all SAEs to the Sponsor if applicable as per CETU SOP for recording and reporting adverse events.

Serious Adverse Events (SAEs) that are related to the study (i.e. those that result from administration of any of the research procedures) and are unexpected (i.e. not listed in the protocol as an expected occurrence) will be emailed to the REC using the Non-CTIMP safety report to REC form. These will be sent within 15 days of the chief investigator becoming aware of the event. There is no requirement for annual safety reports in addition to the information provided through the annual progress report.

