HbA_{1c} will be measured with freepost finger prick home testing kits (provided and analysed by The Doctors Laboratory (TDL), United Kingdom, accredited to the international standard for medical laboratories, ISO15189),) which we used successfully in a previous trial.²⁶ The kits will include all of the equipment provided for participants to complete the test at home. Kits will then be posted back via freepost to the TDL team to analyse the samples. No identifiable information will be shared with the TDL team.

Questionnaires

Self-reported questionnaires will be collected via REDCap web surveys, with paper or telephone options available for participants requiring them. Self-reported behavioural and psychosocial measures will be collected via validated questionnaires. Health outcomes and use of health care, medications and weight management services will be collected via self-report.

A full list of questionnaires can be found in Table 2.

Table 2. Full list of questionnaires

Domain	Outcome	Measure	Time point
Clinical	Height	Self-measured	0m
Outcomes	Weight	Self-measured	0m; 6m; 12m; 24m
	Body composition	Self-measured	0m; 6m; 12m; 24m
	HbA1c	Self-measured	0m; 6m; 12m; 24m
Quality of Life	Health-related quality of	EQ-5D-5L ²⁷	0m; 6m; 12m; 24m
and Wellbeing	life		
	Wellbeing	The Short Warwick-	0m; 6m; 12m; 24m
		Edinburgh Mental	

	1	T	
		Well-being Scale (SWEMWBS) ²⁸	
Economic Evaluation	Health Care Use	MODRUM core module with depth questions for medications ²⁹	0m; 6m; 12m; 24m
	Out of pocket weight loss management costs	Selected modified MODRUM depth questions	0m; 6m; 12m; 24m
	Work productivity and impairment	Work Productivity and Impairment Questionnaire ³⁰	0m; 6m; 12m; 24m
Psychosocial factors	Emotional eating	TFEQ-R21 ³¹	0m; 6m; 12m; 24m
	Binge eating	Binge Eating Scale (BES) ^{32,33}	0m; 6m; 12m; 24m
	Experiential avoidance/psychological flexibility	Acceptance and Action Questionnaires (Weight Related) ³⁴	0m; 6m; 12m; 24m
	Depression	Patient Health Questionnaire 8-item (PHQ-8) ³⁵	0m; 6m; 12m; 24m
	Anxiety Stress	Generalized Anxiety Disorder 7-item (GAD-7) scale ³⁶	
	011033	Perceived Stress Scale (PSS-4) ^{37,38}	
Other	Physical activity	International Physical Activity Questionnaire (IPAQ) - Short Form Short form ³⁹	0m; 6m; 12m; 24m
	Sleep quality	Brief version of the Pittsburgh Sleep Quality Index (B- PSQI) ⁴⁰	0m; 6m; 12m; 24m
	Diet intake	Rapid Prime Diet Quality Score Screener (rPDQS)	0m; 6m; 12m; 24m

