4. PLANNED INTERVENTION AND CONTROL

4.1 Supporting Weight Management (SWiM) programme

SWiM (Supporting Weight Management) is a guided self-help programme that uses acceptance-based strategies to support weight maintenance following weight loss. It aims to help people who have lost weight reflect on what has worked (and not worked) in the past, build on what works for them, and learn new strategies to overcome challenges that typically derail weight loss maintenance.

The intervention includes access to an online web platform with 14 modules (SWiM sessions) consisting of psychoeducational content, reflective exercises, and behavioural experiments. Participants will also be provided with the option to receive an adapted paper-based workbook version of the module content. Content is described in Table 3.

SWiM is intended to be a 4-month intervention, with weekly sessions for the first 3 months followed by a one-month break, and a final module at week 17. Participants are encouraged to weigh themselves weekly and to record their weight at the start of each session. Between sessions, participants are asked to complete additional reflective exercises and behavioural experiments as 'SWiM Practice'.

To guide them through the programme, participants receive 4 telephone support calls from a "SWiM coach" over the 4-month programme. Calls are scheduled for week 1 (activation call), week 3, week 8, and week 17. There will also be 3 optional calls that can be used at any time should the participant need additional coach support or be struggling with the intervention.

The coach's role is to help the participant take ownership of their weight management, and the calls are scripted and manualised. Automated email reminders are sent to participants to remind them to complete sessions and calls. If participants are identified as at risk of disengagement (i.e., they have not attended or rescheduled their coach call), the coach will make up to 3 additional re-engagement calls.

Table 3. SWiM Intervention Outline and Content

Week	SWiM Session	Coach support	
1	Welcome to SWiM		
1	Session 1: Planning and Tracking	30-minute scheduled telephone call following completion of SWiM Session 1	
2	Session 2: Control and Acceptance		
3	Session 3: Being Willing	30-minute scheduled telephone call following completion of SWiM Session 3	
4	Session 4: Overcoming Obstacles		
5	Session 5: Being Active and Willing		
6	Session 6: Emotional Eating		
7	Session 7: Stress Management		

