4.2 Control Intervention

No additional structured support will be offered, but participants will be free to use Local Authority- or NHS-commissioned services offered as standard care or self-fund their own methods. Data on this will be captured at all time points so that we can describe the frequency and nature of weight management behaviours in this cohort by intervention type, weight loss programme, and demographics.

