10. SAFETY REPORTING

10.1 AE/SAE Definitions

An adverse event (AE) is any untoward occurrence in a participant that occurs as part of a test procedure whether related to that procedure or not. Test procedures include direct measurements, be they at a testing site or in a free-living environment. For example, a participant who faints whilst having a blood sample taken is experiencing an AE. Monitoring these events enables us to improve our test procedures and responses to future events.

A Serious Adverse Event (SAE) is any untoward medical occurrence or event that either:

- Results in death or is life-threatening
- Requires hospitalisation or prolongation of existing hospitalisation
- Results in persistent or significant disability or incapacity
- Consists of a congenital anomaly or birth defect
- Is otherwise considered medically significant by the investigator

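### SAEs are reportable on awareness, but no safety question is scheduled for both arms and only SWiM participants have scheduled calls before month 6, so SAE counts by arm are liable to unequal ascertainment

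*Protocol*

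**What the plan says.** Section 10.1 defines an adverse event narrowly, as "any untoward occurrence in a participant that occurs as part of a test procedure whether related to that procedure or not". The SAE definition that follows has no such limit and includes any event requiring hospitalisation. On timing, section 10.2 says "The Sponsor expects that adverse events are recorded from the point of Informed Consent". Section 10.3 says adverse events are to be "recorded, followed-up and reviewed by an investigator as per the CETU SOP for recording and reporting adverse events", and for serious events: "All Serious Adverse Events will be reported to the Chief Investigator using the CETU SAE form within 24 hours of awareness of the event".

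Contact differs by arm. For SWiM, section 4.1 states: "Calls are scheduled for week 1 (activation call), week 3, week 8, and week 17". It adds three optional calls with no fixed time, and up to three re-engagement calls for participants who have neither attended nor rescheduled a coach call. For controls, section 4.2 states: "No additional structured support will be offered".

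Both arms are assessed at 0, 6, 12 and 24 months. Tables 1 and 2 list no adverse-event item at any of these visits. The nearest thing is in section 3.3.3: "Health outcomes and use of health care, medications and weight management services will be collected via self-report". Table 2 places the health-care-use module under economic evaluation, and nothing in the protocol links an answer there to the SAE form.

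**The concern.** An SAE can be recorded only if the study team learns of it. The protocol states when the reporting clock starts but not how events come to light, and it schedules no safety question common to both arms. The planned opportunities for a participant to mention a hospital stay in the first months lie almost entirely in the SWiM arm.

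If SAEs are later tabulated by arm, an early excess in SWiM could be an artefact of contact, or a real excess could be dismissed as one. Unequal ascertainment cannot be reliably undone in the analysis, so the remedy belongs in the data collection schedule before follow-up begins. Two features make the matter harder to resolve later: participants and study coordinators know the allocation, and there is no separate data monitoring committee (section 14).

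**Working it through.** The protocol gives no SAE rate, SAE count or detection probability, so there is no figure of its own to reproduce on this point. The check has two parts.

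**1. Scheduled routes to awareness, from the randomisation call to month 6**

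| Route | SWiM | Control | Source |
|---|---|---|---|
| Scheduled coach calls | 4 (weeks 1, 3, 8, 17) | 0 | 4.1, 4.2 |
| Optional calls, no fixed time | 3 available | 0 | 4.1, 4.2 |
| Re-engagement calls, only if disengaging | up to 3 | 0 | 4.1, 4.2 |
| First follow-up assessment | month 6 | month 6 | 3.3.3, Table 1 |
| Adverse-event item at assessments | none listed | none listed | Tables 1 and 2 |

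The theoretical ceiling in SWiM is 4 + 3 + 3 = 10 calls. Few participants would reach it, because it adds the calls of people seeking extra support to those of people disengaging. Nor is 4 a minimum, since scheduled calls can be missed.

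**2. What unequal detection would do to the counts (illustration only)**

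Inputs: 1,840 / 2 = 920 per arm (sections 3.2 and 3.1). Assumed: the same true six-month SAE risk of 3% in both arms, so 920 × 0.03 = 27.6 true events per arm. Detection probabilities are d_S in SWiM and d_C in control.

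- Recorded events by month 6 are 27.6 × d_S and 27.6 × d_C. Their ratio is d_S / d_C, whatever the true risk.
- For 24 months, assume a constant rate and control-level detection in both arms after month 6. The ratio is then (d_S + 3 d_C) / (4 d_C).

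| d_C | d_S | Recorded, control | Recorded, SWiM | Ratio at 6 months | Ratio at 24 months |
|---|---|---|---|---|---|
| 0.8 | 0.8 | 22.1 | 22.1 | 1.0 | 1.0 |
| 0.7 | 0.8 | 19.3 | 22.1 | 1.14 | 1.04 |
| 0.5 | 0.8 | 13.8 | 22.1 | 1.60 | 1.15 |
| 0.3 | 0.9 | 8.3 | 24.8 | 3.0 | 1.5 |

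The first row also shows the aim of a common question. If it makes detection equal in both arms, the ratio returns to 1.0.

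**The case against.** The strongest reply is that the 24-hour sentence is a deadline and not a method of finding events. Recording is delegated to a trials-unit SOP that is not shown and may prescribe active elicitation. That stands, and a reader should not infer that SAEs are captured only by chance. But the assessment schedule belongs in the protocol, and this one contains no safety item. A unit-wide SOP cannot be assumed to offset a contact imbalance that this particular design creates.

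Second, the protocol plans no by-arm SAE comparison. Section 10 concerns case-level assessment and ethics-committee notification, and no safety outcome appears in sections 2.2, 3.5 or 5.2. This also stands. A reader might infer that the trial's safety conclusions are already biased against SWiM, but the documents do not support that. They show only that any SAE summary by arm would inherit unequal chances of detection.

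Third, coach calls are scripted, and nothing says that coaches ask about or pass on SAEs. The direction of bias is therefore likely but not established.

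Fourth, both arms report health outcomes and health care use at 6, 12 and 24 months, and no text confines those answers to the economic evaluation. They could even out detection of admissions if they were linked to SAE reporting. The protocol neither states that link nor says whether the module covers admissions.

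Finally, a reader might be drawn to an extreme illustration. With 80% against 20% detection, the recorded counts are about 22 and 6 (27.6 × 0.8 and 27.6 × 0.2), with a two-sided exact binomial p of about 0.004. At 80% against 60% they are about 22 and 17, with p about 0.5. Both rest wholly on assumed rates, so neither shows that a false significant excess is to be expected.

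**Conclusion.** The contact imbalance and the absence of a shared safety item are plain in the text. Following the schedule as written gives the arms unequal opportunities for an SAE to come to light, concentrated in the roughly four months of the SWiM programme within a 24-month follow-up. Recorded SAEs are liable to be higher in SWiM early on, for reasons unrelated to true risk.

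The protocol does not allow the size to be computed. Under equal true risk, the assumed detection pairs give six-month ratios from 1.0 to 3.0 and 24-month ratios from 1.0 to 1.5. The 24-month figures also assume a constant event rate and equal detection after month 6. The point concerns comparisons of SAE counts. It does not touch the primary weight analysis or the case-by-case reporting of related, unexpected SAEs. It is worth correcting because the correction is simple before follow-up starts and cannot be reliably made afterwards.

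**What to change.** 1. Add to Tables 1 and 2, and to sections 10.2 and 10.3, one identically worded question on serious events and hospital admissions at 6, 12 and 24 months in both arms. Put it in the minimal data questionnaire too, which section 3.3.3 describes as holding only the primary outcome and key process data. A positive answer triggers the SAE form.
2. Add a source-of-report field to the SAE form: questionnaire, coach call, spontaneous, other.
3. State that any by-arm SAE summary takes as its main comparison the events elicited identically in both arms, plus deaths from any source. All SAEs should also be tabulated by arm and source, with questionnaire response shown by arm.

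Deaths need the explicit provision because participants cannot report them in a questionnaire. Response by arm is needed because section 5.1 assumes 30% attrition, and differential response would bring back unequal ascertainment in another form.

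The cost is one question, one field and some protocol wording, together with a real increase in SAE forms. At an assumed 3% per six months, 1,840 × 0.03 × 4 = 220.8, so up to about 220 forms over 24 months before attrition. The trial team should plan for that workload.

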11. RESEARCH GOVERNANCE AND APPROVALS

The investigators will ensure that the trial conduct conforms to the principles of the Declaration of Helsinki (2024), ICH notes for Guidance on Good Clinical Practice and the Data Protection Act. All research participation will be done under written informed consent.

The protocol, participant information sheets, and e-consent form will be submitted for HRA approval from the Research Ethics Committee. No participants will be recruited until relevant approvals have been received. Where needed, the Investigators will submit any proposed substantial and non-substantial amendments to the protocol or other approved documents to the HRA for approval. Substantial amendments will not be implemented until relevant approvals have been given.

Sponsor:

The study will be sponsored by the University of Cambridge and Cambridgeshire and Peterborough ICB and is funded by the National Institute of Health Research. The University of Cambridge will provide indemnity in the case of negligent and non-negligent harm for research conducted through its Units when it is Sponsor and for employees or others acting on behalf of the University.

Insurance:

The University of Cambridge will arrange insurance for negligent harm caused as a result of protocol design and for non-negligent harm arising through participation in the study.

The University Insurance Manager has advised that insurance for negligent and non-negligent harm under the University's Clinical Trials policy can be arranged if this study is approved by an NHS Research Ethics Committee.

13. PATIENT AND PUBLIC INVOLVEMENT

Substantial PPI input has already contributed to the development and evaluation of the SWiM intervention, and we will continue to seek PPI input from our Patient User Group Panel (PUGP), which comprises members with diverse experiences of weight loss and weight maintenance.

To maximise participant engagement and retention, and minimise burden, PPI representatives have also reviewed the content, design, and delivery of participant-facing materials. They will also advise on the content and methods of questionnaires and qualitative interviews to ensure sensitivity and to maximise participant engagement.

A member of the PUGP will review the transcripts of the qualitative interviews, providing input to the analysis and interpretation of the findings. They will be included as a co-author on the qualitative results paper.

Two PPI representatives ([name] and [name]) are Investigators on the trial, have contributed to the design of the protocol and chair the PUGP. They will also contribute to designing and delivering PPI training, preparing ethics and R&D submissions, co-authoring journal articles and the final report, disseminating findings to a wide range of audiences, and supporting other PPI members.

One PPI representative will be a member of the Programme Steering Committee. The representative will review the final study reports and contribute to the writing of specific sections, such as the lay summary.

Including PPI perspectives in plans for dissemination will ensure that we access an appropriate range of audiences and communicate messages effectively. PPI representatives will advise on content and methods of dissemination and will review public facing documents such as newsletters and press releases.

PPI representatives will be reimbursed for their time and expenses in a timely manner and tailored PPI training will be provided to suit the specific needs of the individual and their role. We will use the INVOLVE Standards for PPI as a guide.

14. PROGRAMME STEERING COMMITTEE

The Programme Steering Committee (PSC) will provide overall supervision for the SWiM 2.0 Trial on behalf of the Trial Sponsors (University of Cambridge) and Trial Funder (NIHR) and ensure that the project is conducted to the rigorous standards set out in the UK Policy Framework for Health and Social Care Research and the Guidelines for Good Clinical Practice. The Programme Steering Committee will also take on the role of Trial Steering Committee (this is a low-risk trial, and a separate Data Monitoring and Ethics Committee is not deemed necessary).

The PSC will provide advice to the Investigators on all aspects of the trial and will review and agree the trial protocol, the statistical analysis plan, and any amendments to the protocol. The PSC will be chaired by [name] (University of Bristol). Independent members include [name] (AstraZeneca, Statistician), [name] (National University of Ireland Galway, Health Economist), and [name] (PPI Advocate). This is a low-risk trial with no rules for early stopping and participants and study coordinators are not blind to intervention allocation. Thus, a separate data monitoring committee was not deemed to be necessary.

15. DISSEMINATION

At the end of the trial, we will present our findings to our PPI representatives and our stakeholder panel and identify appropriate ways to communicate findings to participants and other non-academic audiences.

All specified analyses will be written up as scientific papers and submitted for publication in peer-reviewed open-access journals. Members of the research team will be involved in reviewing drafts of the manuscripts, abstracts, and any other publications arising from the trial. The Principal Investigator will have final approval on all publications and press releases. Authorship will be determined using ICMJE criteria.

In all papers or reports for publication the following statement (which incorporates a disclaimer in view of the independence of the research) should be used, amended accordingly, depending on the type of output:

"This study/project is funded by the National Institute for Health and Care Research (NIHR) Programme Grants for Applied Research (NIHR 206801). The views expressed are those of the author(s) and not necessarily those of the NIHR or the Department of Health and Social Care."

The lead author must also give NIHR notice of any media activity (e.g. press release of research) and a copy of the press release at least 3 days before release.

